Protocol for Sample Size / **Power calculations for surveys:** Simulations were run to determine the achieved power of our multiple baseline design resulting in an average of 240 participants per site for surveys collected at the beginning and end of four academic semesters at UHM and UHH and five academic semesters for HPU (20 data points, total n = 4,800). We assigned 60% of the students at baseline to already be a DOD (prior to being exposed to the intervention), based on the proportion we observed in previous work. Using an α =0.05 (two-sided) and a power of 80%, a simulation of 500 iterations found that the minimum detectable difference (MDD) in DOD prevalences comparing the 9 pre- and 11 post- intervention assessments, using our analysis approach, was 4 percentage points for an average change overall (3 campuses) and was 7 percentage points within a single campus; this was true assuming no change or a 3 percentage point drift in the pre-intervention prevalences over time.

Protocol for recruiting students for Study Surveys and Intervention activities Before taking the iDecide survey, students had to confirm they had read the consent form and actively consent (click yes). Eligibility was the verified. Only undergraduates enrolled at the three participating universities (UHM, UHH, HPU) were eligible, with enrollment verified by the respective university. Age was the only other eligibility criteria (18 years or older). Of the 8,001 online

consent forms completed, 853 (10.7%) reported enrollment at a nonparticipating university, and 2,073 (25.9%) didn't finish the survey. After verifying enrollment status for the remaining 5,075 survey entries, 248 (4.9%) were excluded because the student was not currently enrolled or was a graduate student, or their survey was a duplicate within that assessment; 4,837 was the final count.

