Protocols included total of 15 to 22 contests per site per semester were held during the intervention, with the largest number of contests (n=58) being held in the Spring of 2016 when all three sites were active in the intervention (see Figure 1). As an indicator of the dose for our gamification protocol, up to seven Instagram picture contests and six Instagram caption contests were held per semester, and five YouTube/Instagram video contests. Additionally, an essay (first person "reporter" story) contest and a pledge contest (members and any currently enrolled student could pledge on behalf of a specific RIO to become a DOD on next license renewal). In addition, two random drawings were held: one in the first week of classes at a campus center table, and another at the end of a semester for contest entrants who entered but did not win a contest. Finally, a referral program was created where those who won a contest more than two times in one semester (and, thus, were no longer eligible to enter that semester) could win a prize by referring another student to enter a contest if that student subsequently won. There were nine themes for the Instagram picture/caption contests, and five themes for Instagram/YouTube (15-60 seconds) video contests.

Table 1 (see next page) lists the specific intervention protocols / themes for each contest on a social media site.

Table1: Organ donation related themes for Social Media contests			
Theme	Instagram picture contest	Instagram Caption contest	YouTube video contest
Hug a Heart!	Sp2015 Fa2015 Sp2016 Fa2016	Sp2015 Fa2015 Sp2016 Fa2016	
Go green recycle yourself!	Sp2016	Sp2016	Sp2015 Fa2015 Fa2016
Be a SUPER HERO! Organ donors can save 8-20 people	Sp2015 Fa2015 Fa2016	Sp2015 Fa2015 Fa2016	Sp2015 Sp2016
What are the odds? You're more likely to need an organ transplant than to be a donor when you die	Sp2015 Sp2016	Sp2015 Sp2016	Sp2015 Fa2015 Fa2016
Bust a myth! Find a myth about organ donation and expose the truth	Sp2015 Fa2015 Fa2016	Sp2015 Fa2015 Fa2016	Sp2015 Sp2016
Not as many as you think! Only 20% of Hawaii college students are designated organ donors	Sp2015 Fa2015 Fa2016	Sp2015 Fa2015 Fa2016	
I'm gonna tell MOM! Talk to your mom (and other family) about your wishes to be a donor	Sp2015 Fa2015 Sp2016 Fa2016	Sp2015 Fa2015 Sp2016 Fa2016	Sp2015
This is what a donor looks like	Sp2015		

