The primary analysis models were repeated in the longitudinal sample, accounting for repeated measures. Further, a logistic model of post-intervention DOD status was performed among the longitudinal sample where the students never reported being a DOD at any pre-intervention assessment. All post repeated measures for these individuals were included in one model (allowing for repeated yes answers) and all post repeated measures up until when the first yes reported for DOD was included in a second model. The independent variables included the assessment indicators, age, sex, ethnicity and religion. The predicted percentage adopting DOD would be obtained from the model and tested against 0 using a t-test. This comparison was repeated for each post-intervention time (e.g., 1st post-test) and for each school, as well as by subgroups defined by covariates. A similar analysis was performed for the "talk to parents" outcome in the subset who never reported having this conversation on any pre-intervention survey.

Lastly, in order to determine if the intervention was more effective in students less likely to be a donor, protocols stratified the statistical analyses using a "propensity score" based on static student characteristics. We anticipated that students with characteristics making them less likely to become a DOD might be more influenced by our intervention. Propensity scores were developed for DOD status by using a logistic regression of DOD status using pre-intervention data to determine predictors from among demographic/sociocultural variables (e.g., age, sex, race, religion, place of birth, years lived in HI, college year, tuition source, college major, college credits, recruitment method, study site and time). The resulting DOD model based on 2129 surveys (Donor: Yes=1137, No=992) included significant factors of age, sex, race, college year, religion, and tuition source, using stepwise variable selection. The resulting logistic regression equation would then be applied to all surveys to obtain predicted probabilities that were used as "propensity scores." The primary analyses for the cross-sectional data set was performed separately for surveys with a low propensity score < 50% and for surveys with a high propensity score ≥ 50%. The analyses for the longitudinal data set were also stratified by low and high pre-intervention propensity scores, based on the average for students who provided ≥ 1 pre-test survey.

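### Adoption among prior non-donors is tested against 0, which is not the no-intervention expectation, so rejection does not show an intervention effect

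*Combined protocol and SAP*

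**What the plan says.** The Statistical Analyses Protocols section first repeats the primary pre/post models in the longitudinal sample. It then adds an adoption analysis: "a logistic model of post-intervention DOD status was performed" among "the longitudinal sample where the students never reported being a DOD at any pre-intervention assessment". There are two versions. One keeps every post-intervention survey and allows repeated Yes answers. In the other, "all post repeated measures up until when the first yes reported for DOD was included in a second model". The covariates are the assessment indicators, age, sex, ethnicity and religion.

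The inference for both versions is: "The predicted percentage adopting DOD would be obtained from the model and tested against 0 using a t-test". The test is repeated for each post-test, each school and covariate subgroups, and the longitudinal analyses are also stratified by propensity score. A similar analysis is planned for the talk-to-parents outcome, among students who had reported no such talk before the intervention.

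Two other places bear on the choice of null. The power section gives its detectable differences under two scenarios: "this was true assuming no change or a 3 percentage point drift in the pre-intervention prevalences over time". The contest section describes a pledge contest in which students "could pledge on behalf of a specific RIO to become a DOD on next license renewal".

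**The concern.** The starting adoption rate is 0 because of how the students are selected, and every modelled record is post-intervention. Covariate adjustment therefore cannot supply the rate that would have been seen without the intervention. Testing against 0 asks whether any prior non-donor later said Yes. That would be a test of the intervention only if nobody switched for any other reason, and the plan does not argue this. A logistic model's predicted probability also exceeds 0 by construction, so the null is not a meaningful value within the model.

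Switching without the intervention is plausible from the outcome itself, which is self-reported status on a licence, ID card or registry. Licences are issued and renewed whether or not the project runs, and self-reports can be inconsistent. Even if overall prevalence is stable, No-to-Yes switches may be offset by Yes-to-No switches, and selecting prior non-donors keeps only the first kind. Stopping at the first Yes deals with repeated Yes answers but leaves the null unchanged.

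At stake is a significant adoption result being reported as caused by the intervention, overall and again by school, subgroup and stratum.

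**Working it through.** **1. The plan's own design figure.** The power section gives a minimum detectable difference of 4 points from a 60% baseline, with 9 pre and 11 post assessments averaging 240 participants each. That is 9 × 240 = 2,160 pre and 11 × 240 = 2,640 post. A two-proportion test of 60% against 64% at two-sided 5% has power 81.1% by formula and 81.1% by simulation (no drift), against the stated 80%. The figure reproduces. It concerns the pre/post contrast; no design figure is given for the adoption test.

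**2. How many Yes answers reject the null of 0.** Take one record per student, n students, x Yes answers and p = x/n. The Wald statistic is t = p / √(p(1−p)/n) = √(x / (1 − x/n)).
- x = 4: t is always above √4 = 2, so it exceeds 1.96.
- x = 3: t exceeds 1.96 only if 3/(1 − 3/n) > 3.84, that is n < 13.7.

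So from n = 20 to n = 992, four Yes answers are needed and are enough.

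**3. Rejection with no intervention effect.** This is P(X ≥ 4) for X ~ Binomial(n, q), where q is the background switching rate. Both n and q are assumed, because the documents give neither.

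| q | n=20 | n=50 | n=100 | n=200 | n=300 |
|---|---|---|---|---|---|
| 2% | 0.1% | 2% | 14% | 57% | 85% |
| 3% | 0.3% | 6% | 35% | 85% | 98% |
| 5% | 2% | 24% | 74% | 99% | 100% |

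**4. An illustration from the plan's own numbers.** Suppose the 3-point drift were upward and came wholly from No-to-Yes switching. At the assumed 60% baseline it would be 3/40 = 7.5% of non-donors. The propensity-score paragraph reports "The resulting DOD model based on 2129 surveys (Donor: Yes=1137, No=992"), which is 992/2129 = 46.6% No and gives 3/46.6 = 6.4%. Rejection at 6.4% and 7.5% would be 40% and 52% at n=50, and 89% and 95% at n=100.

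**5. Bound on the subset.** The 992 are surveys, not students. Membership also requires a later post-test and no Yes on any pre-test, so the subset is probably well below 992.

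**6. Check on the one-record simplification.** Simulated data (600 sets per cell) were fitted with a logistic model with two covariates, followed by a student-clustered delta-method test of the mean predicted percentage. The assumptions were 60/30/10% of students with 1/2/3 post surveys and background switching per survey. Rejection at n=50/100/200:
- Stop at first Yes: about 7/35/83% at 2% background and 50/95/100% at 5%.
- Repeated Yes allowed: about 6/26/76% at 2% and 46/91/100% at 5%.

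These exceed step 3, as expected when students have more than one occasion to switch.

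**7. With a comparator.** With no intervention effect, a two-sample test against an unexposed switching rate rejects 4% to 6% of the time (50 to 200 per group, q from 5% to 15%).

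**The case against.** The plan nowhere says that rejecting 0 demonstrates an intervention effect. It ties the primary hypothesis to the pre/post comparison and adds the adoption model afterwards. On that reading the test is a supplementary description, and one sentence calling it uncontrolled would do. It is true that the plan makes no such claim, and calling these analyses secondary is this review's reading. But the same section stratifies the longitudinal analyses to ask in which students the intervention worked better, which is an effect reading, and a t-test against 0 has no other evident purpose.

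The evidence on size is also thin. The drift is a simulation scenario set beside no change, has no stated direction, and concerns samples that include different students, so turnover alone could produce it. The pledge contest shows an occasion for registering, not a rate. Both points stand: step 4 is illustration only, and the conclusion does not rest on it.

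The plan gives neither the unit nor the degrees of freedom of its t-test. If they came from the 11 post assessments (10 df, cutoff 2.23; an assumption), five Yes answers would be needed at n=50 to 200, and rejection at 5% background would be about 10% at n=50 and 56% at n=100. The size changes, but the direction does not.

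Finally, the longitudinal pre/post repeat can also carry ageing and licence renewal, and the text states no separate calendar-time term. That is a fair limitation of the other analysis, but it does not make 0 a valid null here.

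**Conclusion.** The concern holds, with high confidence, and should be fixed. As written, the adoption test can reject with no intervention effect because its reference value is wrong. That conclusion needs neither the subset size nor the background rate; only the size of the error depends on them. The error is severe if the subset is about 200 or more with 3% to 5% or more background switching (85% to 99% rejection at n=200 in the simplified test). It is low in very small cells, which some school, post-test or subgroup analyses may be. These figures assume a 1.96 cutoff and one independent record per student.

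The problem covers both adoption models, all their repeats, and talk to parents if the similar analysis uses the same null. The primary cross-sectional comparison and its longitudinal repeat do not use this null and are not affected by it.

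**What to change.** Delete the test against 0 for DOD status and for talk to parents, including the repeats by post-test, school, subgroup and propensity stratum. Report the adoption percentages with confidence intervals that account for repeated surveys, and describe them as uncontrolled. Base intervention inference on the pre/post comparison.

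As an optional exploratory addition, where pre-to-pre survey pairs exist, compare No-to-Yes switching between exposed and unexposed consecutive pairs. Use a discrete-time logistic model with elapsed time, calendar semester, campus, age, sex, race/ethnicity and religion, clustered by student. Leave out the 20 assessment indicators, which are collinear with exposure. State the number of unexposed pairs and the limited precision.

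The core change costs SAP wording and one set of tables, with no new data; adoption results lose their p-value. Because the document already reports accrual and survey counts, dropping a documented test should be recorded openly as a change. The exploratory comparison may be too imprecise to help: 80% power at two-sided 5% for a 4-point excess needs about 376 pairs per group (2% vs 6%), 638 (5% vs 9%) or 1,035 (10% vs 14%), before allowing for clustering. A campus that started early may have few or no unexposed pairs.

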I'll do it if YOU do it first! Be an advocate, tell someone you know THEY can save 8 lives and improve the quality for up to 20 more, just by being an organ donor. Spread the word!	Sp2016	Sp2016	

4) Statistical Analyses Protocols

Two types of data sets would be created: a cross-sectional set and a longitudinal set. The cross-sectional dataset would include data from all surveys at each of the 20 assessment points (see Figure 1). The design allowed for students

to complete surveys at more than one assessment point. Due to uniqueness of student email addresses, those with repeat surveys could be identified. Thus, students could complete one or more pre-intervention surveys, one or more post-intervention surveys, or complete both pre and post-intervention surveys. The longitudinal dataset would include only those students who completed one or more baseline surveys and one or more post-test surveys.

The primary hypothesis was that exposure to the intervention would increase the percentage of students who reported being DODs on license and/or who spoke to their parents about their choice to be (or not be) a DOD on their license, and exposure would also improve knowledge and attitudes about OD. The primary analysis of the cross-sectional data used a logistic model of the outcomes DOD status or "talk to parents" regressed on a set of indicator variables reflecting each of the 20 assessment points (time by school combinations), adjusted for student's age, sex, race, and religion. Predicted DOD status (or family talk status) was computed from the model for each assessment point and the predicted statuses were compared between pre-intervention and post-intervention assessments using a t-test to test the primary hypothesis. We also repeated the test within subgroups defined by school and by covariates, such as race, to determine if the intervention effect differed by subgroups. Linear models regressing knowledge and attitude scores on assessment indicator variables and adjustment factors were used to determine the intervention effect on these scores.

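### Whether the effect differs by campus, covariate or donor propensity is judged from separate within-group tests with no test of the difference, and the propensity strata lean modestly toward the expected answer

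*Combined protocol and SAP*

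**What the plan says.** In the combined protocol and SAP, section 4 (Statistical Analyses Protocols), the primary analysis compares model-predicted outcome status before and after the intervention across 20 assessment points. The authors then "repeated the test within subgroups defined by school and by covariates, such as race, to determine if the intervention effect differed by subgroups".

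The end of the same section turns to a donor propensity score, used "in order to determine if the intervention was more effective in students less likely to be a donor". It is a stepwise logistic model of designated-donor (DOD) status fitted to 2,129 pre-intervention surveys (1,137 yes, 992 no). "The resulting logistic regression equation would then be applied to all surveys to obtain predicted probabilities that were used as" the scores, so the surveys that built the model are also scored by it. The stratified step reads: "The primary analyses for the cross-sectional data set was performed separately for surveys with a low propensity score" under 50%, and the same for 50% and over. The plan says in advance that it expects unlikely donors to respond more.

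No interaction, between-group contrast, confidence interval for a difference, hold-out or cross-fitting is described. Students may answer more than once, and the section notes: "Due to uniqueness of student email addresses, those with repeat surveys could be identified".

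The sample size section says the minimum detectable difference "was 4 percentage points for an average change overall (3 campuses) and was 7 percentage points within a single campus", at two-sided 0.05 and 80% power.

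**The concern.** There are two linked problems.

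1. **No test of the difference.** Both stated aims are comparative. Separate results in two groups do not test whether the groups differ: one can be significant and the other not when the true effects are equal. The plan gives no other rule for deciding, so a uniform effect could easily be reported as effect modification.

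2. **The strata are built from the outcome being compared.** The score follows chance in the pre-intervention donor answers, and those same surveys are then sorted by it. Observed pre-intervention prevalence is therefore somewhat too low below 50% and somewhat too high above it. Post-intervention surveys share that chance only as far as the same students return. The low stratum then appears to rise and the high stratum to fall with no intervention effect, which is the pattern the authors expect.

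**Working it through.** **Reproducing the plan's figures.** Inputs from the sample size section: 240 surveys per assessment, 9 pre (2,160) and 11 post (2,640), 60% donors at baseline, two-sided 0.05, 80% power. The pooled two-proportion formula gives a detectable difference of 3.94 points (power 81.1% for 60% against 64%), so the stated 4 points reproduces. One campus at a third of the surveys (720 against 880) gives 6.8 points (power 82.6% for 7 points), which agrees with 7 at whole-point rounding. The exact campus split is in a figure that is not shown.

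**Separate tests under an equal effect.** The implied standard error is SE = MDD / (1.96 + 0.842).

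- Overall: 4 / 2.802 = 1.43 points. One campus: 7 / 2.802 = 2.50 points.
- A stratum holding a share s of surveys has SE = 1.43 / √s, and power = Φ(4/SE − 1.96) for a true 4-point effect.
- Equal strata: SE 2.02, power 51% each. Exactly one significant: p1(1−p2) + p2(1−p1) = 2 × 0.51 × 0.49 = 50%.
- 30/70 split (assumed): SE 2.61 and 1.71, power 33.5% and 64.9%. Discordance = 0.335 × 0.351 + 0.649 × 0.665 = 55%.
- Three campuses: power = Φ(4/2.50 − 1.96) = 36% each. Mixed verdicts = 1 − 0.36³ − 0.64³ = 69%.

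A direct test of the difference would be falsely positive in 5%.

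**Lean of the score strata.** Null simulation with 2,129 pre surveys, 4,837 − 2,129 = 2,708 post surveys (assumed split), prevalence 1,137/2,129 = 53.4%, and the cut at 0.50. Also assumed: six factors coded in 18 terms, linear-predictor SD 0.5 to 0.7, returning students keep their status, and an unclustered test. There was no variable selection, and 1,500 replicates were run (Monte Carlo SE about 0.05 points).

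| Post surveys from students surveyed before | False low-stratum rise (points) | Significant rise (nominal 2.5%) | Rise if 20% of pre surveys are second surveys (points) |
|---|---|---|---|
| 0% | +1.1 to +1.4 | 8-9% | +1.6 to +2.1 |
| 25% | +0.9 to +1.2 | 3-5% | +1.2 to +1.6 |
| 50% | +0.6 to +0.8 | about 1% | +0.8 to +1.3 |

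The high stratum moves by −0.4 to −1.0 points.

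Sensitivity (600 replicates), at 0/25/50% overlap:

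- Stronger predictors (SD 1.0): +0.8, +0.8 and +0.4 points.
- Backward selection with six noise factors added: +1.4 to +1.9, +1.1 to +1.4 and +0.7 to +0.9.

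Other outcomes and data sets:

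- The family-talk outcome, if it copies donor status in 30-50% of students: +0.4 to +0.7.
- The longitudinal set, with 0-30% of students re-drawing their status: 0 to +0.4.

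**Does an interaction test alone suffice?** A smaller simulation (120 runs per setting, stepwise selection, no returning students) tested the low-versus-high difference on the in-sample strata. It rejected in 11-19% of runs when the true effects were equal. With cross-fitted scores it rejected in 3-7%, within simulation error of 5%.

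**The case against.** The strongest reply is that the plan never says a difference will be declared when one group is significant and another is not. The authors might compare estimates, so 50-55% and 69% are rates of discordant verdicts, not of false claims. That reading of the figures is right. But the plan offers no procedure for comparing estimates either, and it presents the repeated tests as the means of deciding.

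On the score, the largest lean requires few or no returning students. The plan defines a longitudinal data set and re-contacted consenting respondents, so overlap is above zero. At 50% overlap the lean is under one point in the base case, against a stratum standard error of about 2 points or more. Its size also rests on inputs the documents do not give. This stands, and it is why the second problem is called modest.

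A logistic interaction tests log-odds, whereas the plan reports percentages. A 4-point rise is about 0.16 on the log-odds scale from 42% and 0.17 from 62%, so this matters little for the strata. It matters more for a subgroup with extreme prevalence: 0.16 from 40% against 0.27 from 80%. The scale should be stated.

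Finally, these are secondary analyses and a direct test has low power. That is a reason for cautious claims, not for leaving the difference untested.

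**Conclusion.** Both parts hold. The absence of any between-group test follows from the text alone and needs no assumption. Its consequence is that an identical 4-point effect gives conflicting stratum verdicts in about half of trials and conflicting campus verdicts in about 70%. These figures take the plan's detectable differences at face value and assume a low stratum of 30% to 50% of surveys.

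The lean of the strata is certain in direction but not in size. Across the settings tried it was about 0.4 to 2.1 points in the low stratum, depending on predictor strength, overlap, repeat surveys and selection. It concerns the cross-sectional donor comparison. It should be weaker for family discussion and for the longitudinal set, does not apply in the same way to the adoption test against zero, and leaves the primary overall comparison untouched.

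The plan should be changed, but the trial's main result does not depend on it. Confidence is medium because of the assumed inputs to the second part.

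**What to change.** **Test each difference directly.**

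- *Campus:* contrast the mean of post minus the mean of pre between campuses, using the 20 existing assessment indicators. A post-by-campus term adds nothing, because it is collinear with them (rank stays at 20).
- *Covariates and score stratum:* add the subgroup main effect where it is absent, plus a pre/post-by-subgroup interaction. State the scale. Converting the result to a difference in predicted percentages matches the plan's reporting.
- Cluster standard errors by student, give the difference with a 95% CI, and claim effect modification only from that test.

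**Cross-fit the score by student.** Split students into 5 folds. Repeat selection and fitting without the held-out students, score all their pre and post surveys with that model, then stratify. Label the result exploratory. In the main simulation this brought the false low-stratum change to between −0.15 and +0.13 points at every overlap. Smaller checks gave values within about 0.3 points of zero.

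**Cost.** No new data and modest programming. Cross-fitting makes the strata slightly noisier and replaces one scoring equation with five, so students with the same characteristics may fall in different strata.

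Precision will look poor. From the plan's detectable differences, before any clustering adjustment:

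- Low versus high: SE = √(2.02² + 2.02²) = 2.86 for equal strata, or √(2.61² + 1.71²) = 3.12 for 30/70. The CI is ±5.6 to 6.1 points, with 80% power only for 8 to 8.7 points.
- Two campuses: SE = 2.50 × √2 = 3.53. The CI is ±6.9 points, with 80% power for 9.9 points.

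Fewer subgroup claims will survive.
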